6.3. Vital Signs

Descriptive statistics (N, mean, standard deviation, median, and range) will be reported for systolic and diastolic blood pressure (SBP and DBP) and pulse at each scheduled time point for absolute value and for change from baseline. In addition, a listing of subjects with abnormal vital signs (temperature, respiration rate, pulse rate, diastolic blood pressure and systolic blood pressure) will be presented with change from baseline vital sign values.

Vital sign parameters will be considered abnormal by using the criteria listed below.

Markedly Abnormal Blood Pressure by Age and Gender				
Age (years)	Male		Female	
	Systolic BP (≥ value)	Diastolic BP (≥ value)	Systolic BP (≥ value)	Diastolic BP (≥ value)
6	105	68	104	68
7	106	70	106	69
8	107	71	108	71
9	109	72	110	72
10	111	73	112	73
11	113	74	114	74
12	115	74	116	75
13	117	75	117	76
14	120	75	119	77
15	120	76	120	78
16	120	78	120	78
17	120	80	120	78
≥ 18	120	80	120	80

Note: Age here is the calculated age at visits (when lab samples are taken).

Markedly Abnormal Heart Rates by Age

Age (years)	Abnormal low value (less than)	Abnormal high value (greater than)
6- <11	65	115
11- <16	55	110

16- <21	55	105
21 and older	45	85

7. CLINICAL PHARMACOLOGY

7.1. Pharmacokinetics

Pharmacokinetics (PK) samples for measuring serum golimumab concentrations will be collected from all subjects at the specified visits as shown in the schedule of events of the protocol. All PK evaluations will be based on the subjects who receive at least 1 injection of golimumab (PKE analysis set). No imputation for missing concentration data will be performed.

The data analysis of serum golimumab concentrations includes the following:

- Summary of serum golimumab concentrations at each visit by treatment group
- Summary of serum golimumab concentrations at each visit by age group (≥ 6 to < 12 Years, ≥ 12 to < 21 Years)
- Summary of serum golimumab concentrations by treatment group and by body weight quartiles
- Summary of serum golimumab concentrations by treatment group and by body weight category (< 45 kg, ≥ 45 kg)
- Proportion of subjects without detectable serum golimumab concentration at each visit by treatment group
- Median serum golimumab concentrations plotted over time by treatment group

In addition, the relationship between serum golimumab concentrations, and antibody to golimumab status, safety and efficacy may be explored using graphical displays.

For summary statistics of serum golimumab concentrations, concentration values below the lower limit of quantification will be treated as zero. Once a subject meets one of the following dosing deviation criteria, the subject's data will be excluded from the by-visit data analyses from that point onwards.

Dosing deviation criteria:

- Discontinue SC study agent administration

- Skipped an SC administration
- Received an incomplete/incorrect SC dose
- Received an incorrect SC study agent
- Received and additional SC dose

In addition, if a subject has an administration more than 7 days earlier or later than the scheduled dosing date, the concentration data collected between such a dosing visit and the subsequent dosing visit will be excluded from the by-visit data analyses. For the Week 26 visit, if the PK sampling time deviates more than 3 days earlier or later than the scheduled date, the PK concentration at this visit will be excluded from the by-visit data analyses. Additional exclusions for incongruous PK data to be implemented based on Janssen SOP-07948v2.

Population PK analyses may be performed to characterize the population PK parameters based on the available golimumab concentration data obtained through the Week 52 visit. The population pharmacokinetic approach will also be used to identify and quantify any significant covariates such as demographic characteristics (including but not limited to body weight, ethnic origin, sex, and age) and concomitant medications that have substantial impact on the population pharmacokinetics of golimumab in subjects with T1D. A detailed analysis plan for population PK analysis will be developed separately, and a stand-alone technical report will be written to summarize the results of the population PK analysis.

PK Analyses Presentation

PK analyses will be summarized through Week 52:

For the analyses, a subject is included in one and only one treatment group on the basis of the treatment regimen followed. The description of the treatment group is as follows:

- Golimumab q2w

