3.2.2. Dose Rationale

This study uses a dosing regimen designed specifically for T1D. It is accepted that different diseases may require unique dosing approaches of the same therapeutic to be most efficacious. In the case of the class of TNF α -blockers, there are a variety of dosing regimens that are disease-specific such as a higher dose regimen of SC golimumab for the treatment of UC as compared to that for rheumatic diseases.

The choice of dose and regimen for this study is based upon 3 factors: 1) disease-specific considerations of T1D, 2) modeling based upon the reported efficacy of TNF α inhibition of etanercept in a pilot study in children with T1D, and 3) the sponsor's safety and pharmacokinetic (PK) the experience with golimumab in adults, adolescents and children.⁴⁸ Although, the dose regimen of SC golimumab chosen for the present T1D study has not been studied before, the sponsor's use of golimumab in adult and pediatric subjects with other indications indicate that the overall exposures in this study population are overlapping with previous experience and thus the existing safety profile of golimumab is applicable to this study.

1. T1D Disease-Specific Considerations

In T1D, the destruction of β -cells is rapid at the time of diagnosis and is considered irreversible.^{6,69,73} For aggressive immune-mediated diseases, higher and/or more frequent induction doses of anti-inflammatory therapies followed by lower regular maintenance doses are often used to gain rapid control of rampant disease activity, and then keep it under control. For most autoimmune indications, including pediatric and adult UC and CD, psoriasis, and in some cases RA, TNF α -blockers are administered using an induction regimen followed by maintenance treatment dosing regimen^{14,22,32,59,68} To preserve residual β -cells in newly diagnosed T1D, rapid neutralization of the inflammatory, anti- β -cell response is likely to be key for an effective therapy. Golimumab steady-state concentrations are only achieved after at least 3 months with routine dosing, and with such a regimen continued β -cell destruction may likely occur. It was determined that 2 SC induction doses spaced by 2 weeks would more rapidly achieve a steady-state level and giving the best opportunity to protect residual β -cells. The induction doses will be followed by a lower maintenance dosing in order to maintain steady-state concentrations and continue to prevent further β -cell loss.

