Study agent dosing should be held during the course of a febrile episode and other conditions as detailed Section 10.2. If the febrile episode is mild and transient and the subject does not meet any criteria in Section 10.2, that dose may still be administered as long as it is in the current dosing window (See Section 7.1) otherwise dosing should resume with the next planned dose. Refer to Section 10.2 for dose holding and dosing resumption for other conditions. If subjects/caregivers have a question about the subject status and their ability to be dosed, they are to consult with the study-site investigational team. If subjects/caregivers have a question about the subject status and their ability to be dosed, they are to consult with the study-site investigational team.

Administration of the first 3 doses will occur during study visits (Week 0, 2, and 4). For subjects/caregivers who will be participating in self-administration, training will take place at these visits. It is possible that the device required for induction doses differs from the device required for maintenance doses. Training should be provided on the device intended for maintenance dosing. Prior to allowing at home self-administration, at least 1 successful injection by the subject/caregiver using the device to be used for at home self-administration, must be witnessed by study staff. At the Week 8, 12, 18, 26, 38, and 52 study visits of the double-blind period and Week 12, 20, 28, 36, 44, and 50 study visits of the open-label extension period where study agent will be administered, either subjects/caregivers or study staff may administer the injection.

Following dosing, subjects are to be monitored for at least 30 minutes as detailed in Section 9.1.3 and Section 9.1.5. All data regarding study agent administration including date, time, and anatomic location of injection, study agent dosing device and if there are AEs, reactions or device complications will be recorded. During self-administration, subjects/caregivers are to contact the study-site team in the event of problems or complication including but not limited to signs of immediate or delayed local or systemic reaction (Section 9.9).

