7.1.2. Dosing Windows

All attempts should be made to dose on the scheduled target dosing day, yet it is recognized that due to schedules and other events this may not be possible.

Weeks 2 and 4: Study agent dosing for Week 2 and 4 is to occur ± 1 day of the target-dosing day.

Weeks 6 through 52: For study agent dosed from Weeks 6 through 52, every effort should be made to administer the study agent on the target dosing day or at least should be given ± 3 days of the target day, regardless of whether subjects are participating in self-administration or being dosed at study sites. In situations where subjects cannot dose within this window, the dose can be administered up to 7 days after the targeted dosing day. If the dose cannot be administered within this period, that dose should not be given, and subjects should resume dosing at the next scheduled dosing interval.

Entire study: Throughout the study, administration of sequential study agent dosing's must occur no less than 7 days apart.

Time	Dose Administration Window Around Target Dosing Day*
Required Administration at the Study Site	
Randomization Visit Week 0	N/A
Visits Week 2 and 4	± 1 day
Visits and Dosing Weeks 6 through 52	± 3 days
*Calculated based on 14-day intervals from randomization day. Subjects/caregivers will schedule dosing-only visits to comply with dosing schedule.	

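### One skipped dose removes a golimumab subject from all later by-visit PK summaries, even when the protocol directed the skip, so the Week 52 summary describes a selected subset of unknown size

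*SAP*

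**What the plan says.** SAP 7.1 lists five dosing deviation criteria. One is "Skipped an SC administration". Once any criterion is met, the subject's "data will be excluded from the by-visit data analyses from that point onwards". No time limit is given, and there is no exemption for skips that the protocol directs.

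The same section has a milder rule for timing: "if a subject has an administration more than 7 days earlier or later than the scheduled dosing date", then "the concentration data collected between such a dosing visit and the subsequent dosing visit will be excluded from the by-visit data analyses". After that interval the subject's data count again.

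The protocol directs some doses to be omitted and dosing to continue afterwards:

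- **Protocol 7.1.2 (Weeks 6 to 52):** a dose may be given up to 7 days after target. Beyond that, "that dose should not be given, and subjects should resume dosing at the next scheduled dosing interval".
- **Protocol 6.2:** "Study agent dosing should be held during the course of a febrile episode".
- **Protocol 10.2:** treatment is suspended, with possible resumption, for liver enzyme elevations, significant infections, serious adverse events and study-agent-related severe adverse events. Missed doses lead to permanent discontinuation only after three in a row.

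Protocol 11 bases the PK analyses on all subjects with at least one golimumab dose and one post-dose sample. Protocol 11.4 requires a listing of all available concentrations and documentation of exclusions in the study report.

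**The concern.** The protocol keeps a subject on treatment after a directed skip, whereas the SAP removes that subject from every later by-visit PK summary. The two SAP rules also sit oddly together. A site that complies with protocol 7.1.2 by omitting a dose loses all the subject's later data from these summaries. A site that gives the dose more than 7 days late, against 7.1.2, loses one interval. The SAP gives no reason for the difference.

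The outputs at stake are the SAP 7.1 summaries: concentrations by visit, the age breakdown, the proportion without detectable drug, the median plot, and the weight breakdowns where these are tabulated by visit. Serum concentrations and the PK profile after induction and maintenance dosing are a secondary endpoint. Skips are tied to fever, infection, liver enzymes and adherence, so the subjects who remain are a selected group, and the group can only shrink as the trial goes on.

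**Working it through.** **Inputs from the documents**

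- Doses every 2 weeks from Week 0 to Week 52 (protocol 7.1.1). The stated total of 27 is reproduced: 52/2 + 1 = 27.
- Planned golimumab arm: 81 × 2/3 = 54 (protocol 11.2).
- PK samples are drawn before dosing (Time and Events Schedule), so the Week 52 dose cannot affect the Week 52 sample.
- Skippable doses before the Week 52 sample: 27, minus the Week 0 dose that brings the subject into the analysis, minus the Week 52 dose, which leaves 25. By the same count there are 5 before Week 12, 12 before Week 26 and 18 before Week 38.

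**Assumed input**

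The documents give no per-dose skip probability *p*, so a range is shown. Discontinuations and the other deviation criteria are not counted.

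**Independent skips**

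Share excluded at a visit with *m* earlier skippable doses = 1 − (1 − *p*)^*m*. For example, at *p* = 1% and Week 52: 1 − 0.99^25 = 0.222, so 54 × 0.778 = 42 subjects remain.

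| *p* per dose | Week 12 (m=5) | Week 26 (m=12) | Week 38 (m=18) | Week 52 (m=25) | Remaining of 54 at Week 52 |
|---|---|---|---|---|---|
| 0.2% | 1.0% | 2.4% | 3.5% | 4.9% | 51 |
| 0.5% | 2.5% | 5.8% | 8.6% | 11.8% | 48 |
| 1% | 4.9% | 11.4% | 16.5% | 22.2% | 42 |
| 2% | 9.6% | 21.5% | 30.5% | 39.7% | 33 |
| 5% | 22.6% | 46.0% | 60.3% | 72.3% | 15 |

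**Skips clustered within subjects**

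A beta-binomial model with intraclass correlation ICC has a = *p*(1/ICC − 1) and b = (1 − *p*)(1/ICC − 1). The share excluded is 1 − B(a, b + 25)/B(a, b), where B is the beta function.

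| ICC | *p* = 1% | *p* = 2% | *p* = 5% |
|---|---|---|---|
| 0 (independent) | 22.2% | 39.7% | 72.3% |
| 0.05 | 15.0% | 27.9% | 56.2% |
| 0.10 | 11.6% | 22.0% | 46.5% |

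The size depends entirely on *p* and on clustering. The ordering does not: an exclusion that never ends can only accumulate, so it is largest at Week 52.

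**The case against.** **Skips may be rare.** The protocol leaves room to avoid them. A dose can be up to 7 days late in a 14-day cycle, a dose may still be given within its window after a mild and transient fever, and a first liver enzyme hold awaits a repeat test, preferably within 72 hours. A hold is therefore not automatically a skip. This stands, and it is why the range starts at 0.2%.

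**The restriction has a purpose.** A summary limited to subjects dosed as planned describes exposure on the planned regimen. A late dose is drug received and an omitted dose is not, so some difference in treatment is defensible. This stands as a reason to keep the restricted summary. It does not explain a permanent exclusion after one omission.

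**Other outputs help.** The protocol 11.4 listings and documented exclusions keep the removed data visible. Population PK would use the available concentrations, but SAP 7.1 makes it optional. The SAP therefore commits to no by-visit summary free of the rule.

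**Stronger readings that a reader might infer, and that the documents do not support:**

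- *That the Week 52 summary will lose 20% to 70% of the arm.* This needs an independent skip rate of about 0.9% to 4.7% per dose, and the documents state no rate.
- *That subjects dosed outside the window are simply kept.* Beyond 7 days off schedule they lose that interval's concentrations.
- *That reported exposure is overstated.* A skip long before Week 52 may leave the Week 52 level unaffected, so dropping that subject costs precision without necessarily causing bias. Only recent skips would clearly lower the level.
- *That protocol 3.2.2 supplies a 12-week recovery rule.* It says "Golimumab steady-state concentrations are only achieved after at least 3 months with routine dosing". That is a minimum for build-up under routine dosing. It does not describe recovery after one missed dose.

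**Conclusion.** The concern holds as a minor point. SAP 7.1 excludes a golimumab subject permanently from the by-visit PK summaries after one skipped dose, without exempting skips that protocol 7.1.2, 6.2 and 10.2 direct. A dose more than 7 days off schedule removes one interval. The late-visit summaries thus cover a selected subset with uninterrupted dosing and may not reflect exposure achieved in the arm.

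The Week 52 loss runs from about 5% to 72% for assumed independent skip rates of 0.2% to 5% per dose. For rates of 1% to 5% with ICC 0.05 to 0.10 it is about 12% to 56%. Neither the rate nor the clustering can be read from the documents, and the direction and size of any bias are not established.

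The consequence is confined to descriptive PK summaries. It would be wrong to infer an effect on the Week 52 efficacy result from the fact that the loss peaks at the primary endpoint visit: the primary analysis, the power and the optional population PK analysis do not use this rule.

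**What to change.** In SAP 7.1, before the Week 52 lock:

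1. Keep the restricted by-visit summary.
2. Add a by-visit summary on all available golimumab concentrations, including the proportion without detectable drug, and show the number excluded at each visit.
3. Reconcile the skipped-dose rule with the off-schedule-dose rule. One way is to make the exclusion after a skip time-limited, with a length that the sponsor justifies from its PK model in place of a fixed 12 weeks.

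The cost is a wording change and one extra table on data already collected. The all-data summary will include some concentrations below steady state; presenting it beside the restricted summary makes that visible.

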2. Model-Based Prediction of TNF α Suppression in T1D Subjects

To date golimumab has been studied in 2 pediatric populations; pJIA and pediatric UC. In the study of golimumab in children 2 to 18 years old with pJIA who were being treated with concomitant methotrexate (MTX) the dose was 30 mg/m² SC every 4 weeks (q4w). In the study of golimumab in children 6 to 18 years old with pediatric UC that dose was 90 mg/m² SC at Week 0 and 45 mg/m² SC at Week 2, and 45 mg/m² SC q4w for children <45 kg and 200 mg SC at Week 0 and 100 mg SC at Week 2, and 100 mg SC q4w in children \geq 45 kg. The approved dose of golimumab in adults (those 18 years old and above) with RA, PsA, and AS is 50 mg SC q4w and for UC is 200 mg SC at Week 0, followed by 100 mg SC at Week 2 and then 100 mg SC q4w.

A mechanistic PK/target engagement (TE) model incorporated PK exposure from a previously established population PK model-based on the pJIA population was paired with a target-mediated drug disposition model to assess the interaction between drug and target and to simulate the suppression of TNF α after TNF α -blocker administration. The PK/TE model was developed based on the assumption that the etanercept dosing regimen tested in T1D results in sufficient TNF α neutralization given the positive results observed in the pilot trial in children with new-onset T1D.⁴⁸ The golimumab dosing regimen was designed to approximate the extent of TNF α suppression obtained using the etanercept dosing regimen in this study and accounting for the differences in PK and TNF α binding affinity between golimumab and etanercept. Concomitant use of MTX, which is standard of care in pJIA, reduces golimumab clearance in subjects with this disease, likely due to suppression of anti-drug antibodies.⁷⁷ Subjects with T1D do not receive MTX, therefore, a 56% faster clearance of golimumab in subjects with T1D than pJIA subjects was assumed for predicting the PK profile in the T1D population.

[figure not shown]

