At these visits, subjects will have medical and eDiary review and other assessments per the [Time and Events Schedule](#). Subjects will receive study agent by study staff and should be monitored for at least 30 minutes following injection and be observed for any adverse reactions, including injection site reaction (Section 9.9). In addition, for those who will be administering the injection outside of study visits (“self-administration”), subjects and/or caregivers should continue and complete administration training, including conducting a successful injection by the subject or caregiver using the device to be used for self-injection. If the training was considered successful and the site staff considers that the subject or caregiver can successfully self-administer, the subject will be sent home with study agent injection devices at Week 4, with instructions for handling and storage of drug and used devices. The visit window for these visits is ± 1 day from the target dosing day.

Study Visits Including Study Agent Dosing: Weeks 8, 12, 18, 26, 38, and 52

During Weeks 8 through 52, subjects will return to the site for their scheduled visit, have predose PK/immunogenicity sample drawn, have safety and/or efficacy assessments performed, and receive study agent dosing by site staff according to the [Time and Events Schedule](#). All subject required data, including that recorded via eDiary data, will be reviewed. During these visits, subjects/caregivers who are administering injections are to return used devices and receive additional devices and supplies per the [Time and Events Schedule](#) since the last visit. At these visits, subjects/caregivers will also receive additional device training as needed. During Weeks 12, 26, and 38, subjects are to have their weight and height reassessed to determine if dosing adjustments need to be made for the next interval as described in Section 6.1, with additional training as needed. The visit windows for these study visits are ± 3 days from the target dosing day.

Study Visits for PK Sampling and Clinical Review Only: Weeks 33 and 45

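### SAP 7.1 excludes mistimed PK samples only at Week 26, so the by-visit golimumab summaries are filtered differently at otherwise matching predose visits

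*SAP*

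**What the plan says.** SAP 7.1 plans descriptive concentration tables, among them "Summary of serum golimumab concentrations at each visit by treatment group", with further summaries by age group and body weight, the proportion of subjects without detectable drug, and a plot of medians over time. It then lists what is left out of the by-visit analyses:

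- **Dosing deviations, all visits.** Five are listed, including "Skipped an SC administration". Once one occurs, the subject's later data are excluded.
- **Off-schedule dose, all visits.** The trigger is "if a subject has an administration more than 7 days earlier or later than the scheduled dosing date". Concentrations collected between that dosing visit and the next one are excluded.
- **Off-schedule sample, one visit.** "For the Week 26 visit, if the PK sampling time deviates more than 3 days earlier or later than the scheduled date", that visit's concentration is excluded.
- **Residual clause.** "Additional exclusions for incongruous PK data to be implemented based on Janssen SOP-07948v2". The SOP's content is not given.

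SAP 2.1 assigns data to nominal visits and sets no analysis window.

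Protocol 9.1.3.1 treats the later dosing visits alike: "During Weeks 8 through 52, subjects will return to the site for their scheduled visit, have predose PK/immunogenicity sample drawn". All have a ±3-day visit window; Weeks 2 and 4 have ±1 day. Protocol 7.1.2 lets a dose from Week 6 to Week 52 be given up to 7 days after its target day. Later than that, the dose is not given. Under Protocol 7.1.1, target days are not moved after an off-schedule dose.

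**The concern.** Off-schedule samples are handled differently at visits that the protocol runs in the same way. A predose concentration falls as the interval since the last injection lengthens, so a late sample reads low. At Week 26 such a value is removed. At Week 52, the primary endpoint visit, and at Weeks 8, 12 and 38, the same deviation stays in the table.

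Part of any apparent change between Week 26 and another visit could then come from the filter and not from exposure. Age and weight subgroups are more exposed to this because each cell holds fewer subjects. Values below quantification are set to zero, so a late sample could also move a subject into the undetectable category.

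**Working it through.** No stated figure is at issue. The check has two parts: which samples the written rules reach, and how far a missed sample could be off.

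**1. Reach of the sampling-time rule**

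The protocol's Time and Events Schedule and section 9.1.3.1 give these on-treatment, post-baseline golimumab concentration samples:

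| Visit | Type | Visit window | Sampling-time exclusion in SAP 7.1 |
|---|---|---|---|
| Weeks 2, 4 | predose | ±1 day | none |
| Weeks 8, 12 | predose | ±3 days | none |
| Week 26 | predose | ±3 days | more than 3 days off |
| Weeks 33, 45 | random, no dose | ±7 days | none (not a trough) |
| Weeks 38, 52 | predose | ±3 days | none |

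The rule covers 1 of 7 predose visits. Week 18 is a dosing visit, but the schedule shows no concentration sample there.

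**2. Can a sample fall in the gap?**

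Take a Week 52 visit held 5 days late, with the sample drawn before the dose and the preceding dose on time.

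- The dose is within the +7-day allowance, so it is given and nothing is skipped.
- The off-schedule-dose rule needs more than 7 days, so it is not triggered.
- The sampling-time rule does not name Week 52.
- The sample is kept unless the SOP removes it. At Week 26 it would be excluded.

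Beyond +7 days the dose should not be given, which makes it a skipped dose. The subject should then leave the by-visit analyses from that point. If the protocol is followed, the gap is therefore about 4 to 7 days late.

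**3. Size for one sample**

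No half-life is stated. Two statements in Protocol 3.2.2 give a rough range: "Golimumab steady-state concentrations are only achieved after at least 3 months with routine dosing", and "a 56% faster clearance of golimumab in subjects with T1D than pJIA subjects was assumed". Assume 3 months is 91 days and steady state takes 4 to 5 half-lives.

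- 91/4 = 22.8 days; 91/5 = 18.2 days
- Divided by 1.56: 14.6 and 11.7 days
- Assumed range: about 12 to 23 days

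With single-exponential decline, the ratio of a sample *k* days late to an on-time one is 2^(−k/half-life).

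| Days late | Half-life 22.8 d | Half-life 11.7 d |
|---|---|---|
| 4 | 0.885 (11% low) | 0.79 (21% low) |
| 7 | 0.81 (19% low) | 0.66 (34% low) |

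As a sensitivity check, a half-life of 7 days would give 33% and 50% low.

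**4. Size for a visit mean**

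The frequency of mistimed samples is not in the documents. Assume 5 to 10%, which is 54 × 0.05 = 2.7 to 54 × 0.10 = 5.4 of the 54 planned golimumab subjects.

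- Low end: 5% × 11% = 0.55%
- High end: 10% × 34% = 3.4%

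The mean moves by about 0.5 to 3.5%. A median is moved little by three to five low values in 54.

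**The case against.** The strongest reply is that other safeguards leave little for a wider rule to do. The ±3-day visit window already limits deviations, the dosing-deviation and off-schedule-dose rules run at every visit, and the SOP may catch the rest. Most of this stands as a limit on size. It does not close the gap: the same ±3-day window applies at Week 26, where the SAP still wanted an exclusion, and the late-dosing allowance reaches past it. The SOP is cited for incongruous data. Whether that includes a plausible but mistimed value cannot be told from the documents in either direction.

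A second reply is that trough level depends on days since the last injection, not on the calendar. A Week 24 dose given 7 days late is permitted and not excluded, so an on-schedule Week 26 sample would then be drawn 7 days after a dose and kept. This stands. Week 26 is not clean either, and a rule tied to the scheduled date does not remove this variation.

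The half-life range is also weak. The 3-month statement is a lower bound for routine dosing, and the 56% is relative to pJIA subjects, so combining them gives only an order of magnitude.

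A reader might infer more than the documents support:

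- *That a mistimed sample of any size is kept.* The +7-day limit together with the skipped-dose rule should remove larger delays. One ambiguity remains: the off-schedule-dose rule speaks of data between dosing visits, so it is unclear whether it reaches the predose sample at the late visit itself.
- *That visits cannot be compared.* They are filtered differently; the likely distortion is small.
- *That Week 52 efficacy conclusions are affected.* The antibody comparison in SAP 7.2 sets C-peptide AUC against antibody status and uses no concentrations. Plots of concentration against efficacy are optional, and the exclusions are not said to apply to them at any visit.

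**Conclusion.** The inconsistency is real and minor. As written, a predose sample about 4 to 7 days late is excluded at Week 26 and kept at Weeks 8, 12, 38 and 52, unless the SOP says otherwise, and no reason is given. Weeks 2 and 4 have no sampling-time exclusion either, despite their tighter window.

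The individual shortfall of 11 to 34% rests on the assumed 12-to-23-day half-life, single-exponential decline and an on-time preceding dose. The shift in a visit mean also rests on the assumed 5 to 10% frequency. The consequence is confined to descriptive PK summaries. The primary C-peptide analysis and the comparison of C-peptide by antibody status do not depend on this rule.

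**What to change.** Replace the Week 26 sentence in SAP 7.1 with one rule along these lines:

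> At each on-treatment predose PK visit (Weeks 2, 4, 8, 12, 26, 38 and 52), a concentration sampled outside that visit's protocol window (±1 day at Weeks 2 and 4, ±3 days from Week 8) is excluded from the by-visit summaries. The random samples at Weeks 33 and 45 are not subject to this rule. Excluded values remain in the listings and in any population PK analysis.

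If Week 26 alone is intended, give the reason. In either case, state whether the SOP covers mistimed samples. Show days since the previous injection beside each listed concentration, because the rule does not control that interval.

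The cost is one sentence and one listing column. Protocol 9.7 already requires actual sampling dates and times, and Protocol 7.1.1 requires dosing dates and times. The downside is that a few more samples leave the by-visit tables, including any at Weeks 2 and 4 that are 2 or 3 days off.
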